5.2 Toxicity Criteria, Dose Delays, and Modifications

5.2.1 Toxicity Criteria

This study will utilize the CTCAE version 4.0 for toxicity and Adverse Event Reporting. A copy of the CTCAE version 4.0 can be downloaded from the CTEP home page (<http://ctep.cancer.gov>). All appropriate treatment areas should have access to a copy of

the CTCAE version 4.0.

5.2.2 Dose Delays

For patients who are unable to tolerate the protocol-specified dosing schedule, dose adjustments are permitted in order to keep the patient on study drug. If administration of sirolimus or everolimus must be interrupted because of unacceptable toxicity, drug dosing will be interrupted or modified according to rules described in Section 6.4. Major Events are non-treatment-related grade 3 and 4 pulmonary and non-pulmonary toxicities. Treatment should be delayed for major events if simvastatin may further complicate the non-treatment related event. If a major event requires a delay of treatment, treatment must be delayed until toxicity is resolved (\leq Grade 1 or \leq Baseline). For treatment-related toxicities and major events, if toxicity is not resolved in \leq 4 weeks, patient will be taken off the treatment that is most likely to be related to the toxicity. While this most likely will result in coming off study, at the investigator's discretion patients may continue on single agent therapy, if toxicities are \leq grade 2 and there is some evidence of clinical benefit to the patient.

Table 2A: Approach to overlapping toxicities of simvastatin and sirolimus*

Overlapping Toxicity	Dose Reduce First	Dose Reduce Second
Mucositis	sirolimus	simvastatin
Nausea	sirolimus	simvastatin
Abdominal pain	simvastatin	sirolimus
Infections	sirolimus	simvastatin
Diarrhea	sirolimus	simvastatin
Headache	simvastatin	sirolimus

Table 2B: Approach to overlapping toxicities of simvastatin and everolimus*

Overlapping Toxicity	Dose Reduce First	Dose Reduce Second
Mucositis	everolimus	simvastatin
Nausea	everolimus	simvastatin
Abdominal pain	simvastatin	everolimus
Infections	everolimus	simvastatin
Diarrhea	everolimus	simvastatin
Headache	simvastatin	everolimus

*At the discretion of the treating physician.

5.2.3 Simvastatin Dose Reduction

Any AE of \geq Grade 3 and attributed as possibly, probably or definitely related to simvastatin will result in the dose being held until the AE has resolved to \leq grade 1 or baseline, while sirolimus dosing may continue uninterrupted. If the AE resolves, reinstatement of treatment can occur but at a reduced dose as described in Table 3. If the AE recurs at the reduced dose, treatment will be held until the AE has resolved to \leq grade 1 and when resolved treatment can be reinstated at the next lower dose level. No more than 2 dose reductions are allowed during the maintenance cycles.

Table 3: Simvastatin Dose Reduction Schema

Dose mg/day	Reduce to
20 mg daily	15 mg daily
15 mg daily	10 mg daily
40 mg daily	30 mg daily
30 mg daily	20 mg daily

Toxicities that may be attributable to simvastatin include nausea, abdominal pain, diarrhea, upper respiratory infections, headache, and diarrhea. If any of these AEs occur at grade \leq 2, simvastatin may be continued and the AE managed with supportive care. For any AE with a grade \geq 3, the rules outlined in Sections 5.3 apply for holding of dose, dose reduction, removal from study and reporting requirements.

The main laboratory abnormalities which may result from simvastatin include increased CPK and liver transaminases. Patients who develop increased CPK levels ($> 2X$ ULN) will be followed with weekly CPK levels until the abnormalities return to normal. Simvastatin will be continued if CPK values are decreasing on the following week's blood sample. If persistent elevations ($> 2X$ ULN) occur over two weeks (three assessments), or symptoms such as muscle pain are present, the simvastatin study drug will be stopped. The simvastatin study drug will be stopped immediately if myositis (CPK $> 10 \times$ ULN) is documented at any time.

5.2.4 Sirolimus or Everolimus Dose Reduction

Known sirolimus and everolimus toxicities will not be attributed to simvastatin but will only be attributed to sirolimus or everolimus and will result in the following sirolimus or everolimus dose modifications. Pulmonary toxicity of unexpected severity may be attributed to simvastatin (in addition to sirolimus or everolimus) at investigator discretion. Non-pulmonary toxicities of possible, probable or definite and definite and having an attribution to sirolimus or everolimus will result in the following sirolimus or everolimus dose modifications. Blood counts will be evaluated weekly. Within -3 days prior to sirolimus or everolimus dosing, the patient must have an ANC $> 1.0 \times 10^9/L$ and platelet count $> 75 \times 10^9/L$. All non-pulmonary toxicity grade 3 or 4 (except for mucositis, diarrhea, nausea, and acneiform rash) must have resolved to CTCAE grade \leq 2. If toxicity persists, treatment should be delayed by one week for up to 3 consecutive

weeks. If after 3 weeks of delay, all toxicity has still not resolved, then any further treatment with sirolimus or everolimus should be stopped. Simvastatin may be continued after sirolimus or everolimus has been stopped.

If any non-pulmonary toxicity observed Grade ≥ 3 (except for mucositis, diarrhea, nausea, acneiform rash, and swelling of extremities) and/or if platelets $< 75 \times 10^9/L$ and/or ANC $< 1 \times 10^9/L$, causing delay of two weeks of sirolimus then the dose should be reduced by one dose level (Table 5). For patients requiring more than 2 dosage reductions, sirolimus or everolimus will be stopped. If any non-pulmonary toxicity observed was CTCAE **Grade 4** (except for mucositis, diarrhea, nausea, acneiform rash, and swelling of extremities) then sirolimus or everolimus should be stopped.

Table 4: Sirolimus or Everolimus dose level modification guidelines

Dose reduction	Dose and schedule
Starting dose	10 mg daily
1	5 mg daily
2	5 mg every other day

6. Duration of Participation

6.1 Patient retention and drug compliance

Patient retention will be encouraged in several ways. Extensive contact information will be captured for each patient, at the time of study enrollment. This will include home, work, and cellular telephone numbers. Prior to each study visit, the study staff will contact the patient to remind her about the upcoming study visit. Patients will receive a stipend in the amount of \$25 per study visit, for their participation in the study. A check for the reimbursement of expenses will be issued after each study visit.

The study staff and physician will explain the importance of compliance with the study protocol at each patient contact. If a patient fails to comply with a study visit, the study staff will contact her by telephone. If the study staff is unsuccessful in reaching the patient, a follow up letter will be sent by Federal Express, on two consecutive weeks, seeking follow-up.

Compliance with the protocol and drug administration will be strongly emphasized. Pill counts will be performed at visits and episodes of medication noncompliance will be recorded, including the reason for noncompliance. Patients will receive a calendar to document medication and any side effects experienced that day. If a patient wishes to withdrawal from the treatment phase of the study or has a serious adverse event (SAE) (whether related to study drugs or not), patient follow-up assessments will continue for safety monitoring and to avoid problems associated with missing data. The inclusion of such follow-up data will allow for analysis by intention-to-treat.

If a patient is withdrawn from the treatment portion of the study for any reason, the patient will be strongly encouraged to continue with and complete the remainder of the study assessments, as scheduled.

6.2 Consent for Future Contact

During the consent process, patients will have the option to provide permission for future contact. This permission allows for patient contact information, including their full name, address and telephone number, to be collected. The permission for future contact also allows for possible patient contact regarding future IRB-approved studies. If the patient denies permission, no future contact will be made.

6.3 Consent for Continuing Data Review of Medical Records

During the consent process, patients will have the option to provide permission for future data review of their medical records. This permission allows for study staff to contact the patient (or the patient's caregiver(s)) to obtain medical records and other information for a period of up to two years after the patient has withdrawn from or completed the study. The purpose of this data review is to capture information including but not limited to clinical, radiographic, pathologic, laboratory and pulmonary function data, after the patient has exited the study.

6.4 Consent for Storage of Blood Samples for Future Use

Patients will be asked to consent to the storage of leftover blood and serum samples for future use related to LAM. Patients can refuse without impacting their care or ability to participate in this study.

7. Stopping Rules

7.1 Criteria for Terminating Participation on Study

An intent-to-treat approach will be used in this study. All data acquired prior to patient termination for the following reasons will be included in the primary analysis.

- Withdrawal of patient consent
- Withdrawal by the patient
- Withdrawal by the investigator
- Intercurrent illness or event that precludes further administration of treatment or ability to evaluate lung function (e.g. -mental status change, large pleural effusion).
- Pregnancy or failure to comply with adequate contraception
- Continuing patient non-compliance

Every effort will be made to conduct a final study visit and patients will be followed clinically until all study-related adverse events resolve, the patient's condition stabilizes or the adverse events are determined to be permanently ongoing.

7.2 Criteria for Terminating the Study

Up to ten patients will be enrolled in this study. The maximum duration of patient participation is up to 164 days, including a follow-up phone contact one month after the last study visit. In the event of any death, or Grade III SAE attributable to the study agent, enrollment and treatment will be suspended, pending Data Safety Monitoring Board (DSMB) review.

8. Study Variables and Measuring Methods

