4.1 Study and Timeline Overview

The study will enroll up to 10 evaluable patients over 3-6 months. All study patients will be assigned to a starting dosage of 20 mg of simvastatin daily for a period of two months. If patient tolerability to the 20 mg simvastatin dosage decreases, the dose will be down-titrated to 10 mg daily. Intra-patient dose escalation strategy will be performed only for patients who tolerate simvastatin 20 mg daily and the daily dosage of simvastatin will be escalated to 40 mg daily during months 3 and 4. . Patients who are escalated to 40 mg daily who do not tolerate that dose, will be reduced back down to the previously tolerated 20 mg daily.

The patient will be given a copy of the informed consent form. Patients will be given ample time to read and discuss the consent form with the study staff. The study staff will then answer any outstanding questions asked by the patient. The patient will be offered the option of signing the consent form. Those who agree to participate will undergo the remainder of screening at visit 1.

Prior to starting study drug, pulmonary function tests and chest X-ray will be obtained. The spirometry values obtained that contain the best values for FEV1, FVC and DLCO will constitute the baseline values. Patients will be followed with serial VEGF-D levels collected at each visit over a four month period.

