5.1 Definition of Dose Limiting Toxicity (DLT)

DLTs will be defined by toxicity occurring during the first 5 weeks of this study. A DLT will be any non-pulmonary AE of Grade 3 or higher that is at least possibly treatment-related with the exception of nausea and vomiting which have not been treated with optimal anti-emetic therapy. Any DLT that causes a patient to miss > 28 consecutive days of simvastatin will result in the patient being taken off treatment.

A DLT is defined as a toxicity considered at least possibly related to simvastatin. In this regard, it is important to consider the possibility that co-administration of simvastatin may increase the toxicity of sirolimus or everolimus. Conversely, sirolimus or everolimus might influence the toxicity profile of simvastatin. Thus, it may be difficult to confidently attribute certain observed toxicities solely to either simvastatin and sirolimus, or simvastatin and everolimus. With this potential complication in mind, an attempt will be made to define dose-limiting toxicities (DLTs), which apply specifically to simvastatin. In this study, DLTs will include any possibly, probably, or definitely simvastatin-related Grade 3 or 4 toxicity. Known toxicities specific to sirolimus and everolimus such as mucositis will not be considered dose limiting unless the treating physician considers the toxicity to be exacerbated by simvastatin. Toxicities that will be attributable to simvastatin include but are not limited to abdominal pain, nausea, diarrhea, headache, and infectious complications.

The target DLT rate is $\leq 33\%$. The maximum tolerated dose (MTD) will be defined as a) the dose producing DLT in 2 out of 6 patients, or b) the dose level below the dose which produced DLT in ≥ 2 out of 3 patients, or in ≥ 3 out of 6 patients. Patients will be evaluable for a DLT if they have finished 5 weeks of combined therapies. Patients who are removed from study due to clinical progression prior to the 5 week period will be replaced. Patients will be evaluable for response if they have completed 90% of their expected dose of simvastatin for the 8 weeks. Patients will be evaluated for toxicity if they received at least one dose of simvastatin.

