9.2 Safety Monitoring and Adverse Event Reporting

Patients will be evaluated for safety if they have received at least one dose of simvastatin. The frequency, severity and duration of all adverse events, regardless of cause, will be recorded on the case report forms. The frequency and severity of adverse events will be calculated by patient. The most severe grade of adverse event experienced by patient will be counted once. The duration of adverse events will be calculated by the number of days each event persisted. Adverse events will be tabulated by body system and by severity using the NCI Common Terminology Criteria for Adverse Events v4.0, which can be obtained from the CTEP Website: <http://ctep.cancer.gov/reporting/ctc.html>. Tables will be generated for all adverse events including those that are judged to be possibly, probably or definitely related to the simvastatin.

All adverse events will be reviewed by a DSMB created for this study and composed of pulmonologists [name]., [name], M.D., and [name]. Any serious AE (generally grade 3 or 4 toxicity or defined by lead pulmonologist) will result in patient discontinuation of simvastatin until the DSMB

reviews the case and make a recommendation made regarding re-institution of the study drug.

As this is a safety study with a small number of patients, data will be compiled in descriptive tables of results. A study participation summary will be written for each patient and for trends in the data. Special attention will be given to adverse reactions to the simvastatin and any changes in the pulmonary function testing or the laboratory values outside of normal ranges.

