However, if a hospitalization for an unknown event occurs, it should be considered as a serious adverse event.

Prolongation of hospitalization is defined as any extension of an inpatient hospitalization beyond the stay anticipated/required in relation to the original reason for the initial admission, as determined by the investigator or treating physician.

Preplanned treatments or surgical procedures should be noted in the baseline documentation for the entire protocol and/or for the individual patient.

Disability is a substantial disruption of a person’s ability to conduct normal life functions.

Any serious adverse event or death must be reported to the IRB immediately, independent of the circumstances or suspected cause, if it occurs or comes to the attention of the investigator at any time during the study, through 30 days after the last administration of study drug. Any serious adverse event occurring beyond 30 days after the last administration of study drug must be promptly reported, if a causal relationship to study drug is suspected. The only exception to these reporting requirements are serious adverse events that occur during a pre-randomization/washout run-in period, during which either placebo alone is administered, or no active study drug or protocol-specified background drug is administered.

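### After a related Grade 3 or higher event, Table 3 permits restarting simvastatin at 1.5 times the dose that 3.5.1 sets for intolerance; the 7.2 suspension trigger and, less importantly, Table 4 also have gaps

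*Combined protocol and SAP*

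**What the plan says.** **Simvastatin dose.** Section 3.5.1 starts patients on 20 mg and raises the dose to 40 mg for months 3 and 4 if 20 mg is tolerated. Intolerance of 40 mg leads to 20 mg, and intolerance of 20 mg leads to 10 mg; 4.1 repeats both. Section 3.5.1 also allows 15 or 30 mg, but only for mild side effects that the patient can bear.

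Section 5.2.3 covers events of Grade 3 or higher that are at least possibly related to simvastatin. Such an event "will result in the dose being held until the AE has resolved" to grade 1 or lower, or to baseline. Then "reinstatement of treatment can occur but at a reduced dose as described in Table 3". Table 3 goes from 40 to 30, 30 to 20, 20 to 15 and 15 to 10 mg. A further step down follows if the event recurs, and "No more than 2 dose reductions are allowed during the maintenance cycles".

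**Study suspension.** Section 7.2 states: "In the event of any death, or Grade III SAE attributable to the study agent, enrollment and treatment will be suspended", pending DSMB review. Elsewhere grade 3 is a floor. Section 5.1 defines a DLT as "any non-pulmonary AE of Grade 3 or higher that is at least possibly treatment-related". Section 9.2 says "Any serious AE (generally grade 3 or 4 toxicity or defined by lead pulmonologist) will result in patient discontinuation of simvastatin until the DSMB" has reviewed the case. Section 9.3.1 adds: "Any serious adverse event or death must be reported to the IRB immediately".

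**Background drug.** Section 3.5.1 keeps patients on their existing sirolimus or everolimus dose. Table 4 in 5.2.4 gives one ladder for both drugs: 10 mg daily at the start, then 5 mg daily, then 5 mg on alternate days. The text that invokes this ladder cites Table 5, which holds DLT rates.

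**The concern.** Safety is the primary outcome. Section 3.5.1 says that no human data yet show the combination to be safe in these patients, and 1.4.1 describes shared CYP3A4 metabolism and a rhabdomyolysis case. Dose and stopping rules therefore carry much of the patient protection.

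The main difficulty is one of ordering. A patient who merely tolerates 40 mg poorly goes to 20 mg, while a patient with a related Grade 3 or higher event on 40 mg may be restarted at 30 mg. The doses that 3.5.1 keeps for mild effects are the ones Table 3 assigns to severe ones. An investigator following the protocol has two answers for one patient, and the more cautious one belongs to the lesser problem.

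The second difficulty is that a Grade III event is a stated trigger for suspending the whole study while a non-fatal Grade IV event, which is worse, is not named. The third is that an instruction to drop one dose level cannot be carried out when every listed level is at or above what the patient already takes.

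**Working it through.** The plan states no figure on this point, so the check sets the rules side by side and does the dose arithmetic.

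**1. Simvastatin restart dose.** Inputs are from 3.5.1 and 4.1 (intolerance) and Table 3 (after a related Grade 3 or higher event). Cut = (old − new)/old; ratio = Table 3 dose / 3.5.1 dose.

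| Dose at event | 3.5.1 dose | Table 3 dose | Cut in 3.5.1 | Cut in Table 3 | Ratio |
|---|---|---|---|---|---|
| 40 mg | 20 mg | 30 mg | (40 − 20)/40 = 50% | (40 − 30)/40 = 25% | 30/20 = 1.5 |
| 20 mg | 10 mg | 15 mg | (20 − 10)/20 = 50% | (20 − 15)/20 = 25% | 15/10 = 1.5 |

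A second Table 3 step (30 to 20, or 15 to 10) reaches the 3.5.1 dose. The ratio of 1.5 therefore applies to the first reduction only. Getting to the 3.5.1 dose by this route requires the event to recur and uses both permitted reductions.

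The cross-references do not settle which rule governs. Section 5.2.3 points to a Section 5.3 that does not exist, and 5.2.2 sends background-drug changes to Section 6.4, which concerns consent for stored blood.

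**2. Suspension trigger in 7.2, read literally.**

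| Event | Study suspended under 7.2? | Drug held in that patient under 9.2? |
|---|---|---|
| Any death | Yes | Not applicable |
| Attributable Grade III SAE | Yes | Yes |
| Attributable non-fatal Grade IV SAE | Not named | Yes |

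The gap is confined to the automatic suspension of enrollment and of treatment in the other patients. Their number depends on accrual: "The study will enroll up to 10 evaluable patients over 3-6 months". Assume 10 patients, evenly spaced, with 120 days of treatment each.
- Accrual over 90 days: all 10 have started before the first finishes at day 120, so the peak is 10 − 1 = 9 others.
- Accrual over 180 days, starts every 180/9 = 20 days: 120/20 = 6 on treatment, so 5 others.
- Accrual over 180 days, starts every 180/10 = 18 days: 120/18 = 6.7, so up to 7 on treatment and 6 others.

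**3. Table 4 ladder.** Average daily doses are 10, 5 and 5/2 = 2.5 mg. Each entry is the listed level divided by the patient's own dose; a value below 1 is a reduction.

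| Own dose (mg/day) | Reduction 1 (5 mg/day) | Reduction 2 (2.5 mg/day) |
|---|---|---|
| 10 | 0.50 | 0.25 |
| 5 | 1.0 | 0.50 |
| 2.5 | 2.0 | 1.0 |
| 2 | 2.5 | 1.25 |
| 1 | 5.0 | 2.5 |

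At 2.5 mg/day or less, no listed level is a reduction. The documents do not give patients' doses. The 1 and 2 mg sirolimus tablets and the 2.5 mg everolimus tablet in 3.5.2 show that such doses are possible.

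**The case against.** **Table 3.** Restart is permitted, not required, and only after a hold to grade 1 or baseline, a step that 3.5.1 does not mention. Table 3 can thus be read as a specific rechallenge rule and 3.5.1 as general titration. After a serious event, which 9.2 broadly equates with grade 3 or 4 toxicity, the DSMB recommends whether to re-institute the drug and could advise a lower dose. CPK and muscle problems have their own stop rules in 5.2.3. All doses concerned lie within the 5 to 40 mg range in 1.4.2, and the documents show no harm from 15 or 30 mg. All of this stands and limits the consequences. It does not remove the inversion: the written dose after the more severe event is still the higher one.

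A reader might also infer from Table 5 that the disputed rule is likely to be used. Its printed chances of seeing no DLT among 9 patients, 35.0%, 10.7% and 2.7% at true rates of 11%, 22% and 33%, reproduce as (1 − p)^9 and imply a 65% to 97% chance of at least one. Those rates are illustrative. They cover any DLT in the first 5 weeks, including CPK and muscle events that lead to stopping and patients never restarted, and that window precedes the 40 mg period. They do not estimate how often the restart dose would be used.

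**7.2.** Every other severity rule treats grade 3 as a floor, so *or higher* was almost certainly meant. It would be wrong to infer that a Grade IV event goes unattended: 9.2 holds drug in that patient, the DSMB reviews all adverse events, and serious events go to the IRB at once. What remains is a defect in the wording of a stopping rule.

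**Table 4.** It is headed as guidelines. Section 5.2.4 also delays dosing for up to 3 weeks, stops the drug if toxicity persists, and stops it for most Grade 4 non-pulmonary toxicity, whatever the dose. Blood levels are checked against 3 to 20 ng/ml. It would be wrong to say that the ladder never gets as low as 2.5 mg/day, because its last level averages exactly that. The gap concerns only patients already there or below.

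**Conclusion.** The concern holds, with unequal weight across its parts.

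- **Main point.** Table 3 conflicts with 3.5.1 and 4.1. After a related Grade 3 or higher event has resolved, the permitted first restart dose is 1.5 times the intolerance dose at both levels: 30 against 20 mg and 15 against 10 mg. This rests only on the stated doses. The documents give no basis for how often it would occur.
- **Second point.** Section 7.2 as written omits a non-fatal attributable Grade IV SAE from automatic study suspension. Under the accrual assumptions above, between 5 and 9 other patients could be on treatment at the peak. This is probably a drafting slip, but in a stopping rule it should not be left to interpretation.
- **Minor point.** Table 4 offers no reduction at or below 2.5 mg/day. The number of patients affected is unknown, and the delay and stop rules still protect them.

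None of this changes an analysis. Nor do the documents show that patients would be left without safeguards. The rules need correcting because safety is what the study sets out to establish, and the repair is cheap.

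**What to change.** 1. **Table 3.** After a related Grade 3 or higher event, go from 40 to 20 mg and from 20 to 10 mg. Keep the rows 30 to 20 and 15 to 10 for patients already on those doses. Stop simvastatin if the event recurs at 10 mg. Keep 15 and 30 mg for mild effects, as 3.5.1 intends. The path 40 to 20 to 10 mg fits within the limit of two reductions.
2. **Section 7.2.** Replace the Grade III wording with *Grade 3 or higher SAE*.
3. **Table 4.** State the steps as about 50% and 25% of the patient's own dose. This leaves a 10 mg/day patient unchanged (5, then 2.5 mg/day) and would give, for an assumed 2 mg/day, 1 and then 0.5 mg/day. Hold or stop where no lower dose is feasible. Cite Table 4, not Table 5, in the text.

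The cost is an amendment to one sentence, two tables and a citation, plus IRB review. No patients, visits or tests are added. The 10 and 20 mg doses are already needed under 3.5.1, whereas 15 and 30 mg have to be made up from the listed tablets (10 + 5 and 20 + 10).

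### The only study-wide suspension rule (Section 7.2) covers deaths and Grade III SAEs but, read literally, leaves out a non-fatal Grade IV SAE

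*Combined protocol and SAP*

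**What the plan says.** Section 7.2 (Criteria for Terminating the Study) sets the study-level trigger: "In the event of any death, or Grade III SAE attributable to the study agent, enrollment and treatment will be suspended", pending DSMB review. Adverse events are graded by CTCAE v4.0 (Sections 5.2.1 and 9.3).

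Other sections deal with severe events one patient at a time, and they include Grade 4:

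- Section 5.1, on dose-limiting toxicity: "In this study, DLTs will include any possibly, probably, or definitely simvastatin-related Grade 3 or 4 toxicity".
- Section 5.2.3 holds simvastatin for a related event of Grade 3 or above. On restart it says: "If the AE resolves, reinstatement of treatment can occur but at a reduced dose as described in Table 3". It also says "The simvastatin study drug will be stopped immediately if myositis" is documented, meaning CPK above 10 times ULN.
- Section 9.2: "Any serious AE (generally grade 3 or 4 toxicity or defined by lead pulmonologist) will result in patient discontinuation of simvastatin until the DSMB" has reviewed the case and made a recommendation on restarting.
- Section 9.3.1: "Any serious adverse event or death must be reported to the IRB immediately".

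**The concern.** A suspension rule should become no less strict as events become more severe. Read literally, 7.2 fails that test: Grade III suspends, death suspends, and the non-fatal Grade IV event between them does not. The protocol gives no reason for such an exemption.

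Safety is the primary objective, and Section 3.5.1 states that no human data yet show this combination to be safe in these patients. Section 1.4.1 cites a case of rhabdomyolysis with acute renal failure on simvastatin plus rapamycin. If an event of that kind occurred here, was graded IV and was not fatal, 7.2 would not literally stop the other patients taking the same combination. Nor would it stop new enrollment while the DSMB looked at the case.

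**Working it through.** **Step 1: is there another study-wide rule?** The sections on stopping, toxicity and reporting compare as follows.

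| Section | Grades covered | Who is affected |
|---|---|---|
| 5.1 (DLT, MTD) | 3 or higher; 3 or 4 | Defines terms; no study-level action |
| 5.2.2 to 5.2.4 | 3 and 4 | Doses of the individual patient |
| 7.1 | none stated | Termination of the individual patient |
| 7.2 | death, or Grade III SAE | **Whole study: enrollment and treatment** |
| 9.2 | any serious AE, generally 3 or 4 | Simvastatin of the affected patient |
| 9.3.1 | any SAE or death | Report to the IRB; no pause |
| 10.12 | none stated | Withdrawal of the individual patient; names termination by the funder, with no safety criterion |

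Only 7.2 suspends the study, and it is the only severity-based rule here that omits Grade 4.

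**Step 2: follow one event through the rules.** Take a non-fatal, attributable Grade IV SAE. Section 5.2.3 holds that patient's dose, 9.2 keeps her off simvastatin until the DSMB recommends, and 9.3.1 sends the event to the IRB. It is neither a death nor Grade III, so 7.2 as written does nothing for the other patients.

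**Step 3: how many others would be exposed?** The plan gives no figure to reproduce. The inputs are up to 10 patients over 3 to 6 months (Section 4.1: "The study will enroll up to 10 evaluable patients over 3-6 months") and 120 days on drug (Protocol Summary). Three assumptions are added: all 10 enroll at equal spacing of s days, nobody interrupts treatment, and the event is equally likely on any of the 10 × 120 = 1,200 patient-days on drug. Spacing is 90/10 = 9 or 90/9 = 10 days for three months, and 180/10 = 18 or 180/9 = 20 days for six.

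For two patients whose entries are d places apart, there are 10 − d such pairs. Their on-drug periods overlap by max(0, 120 − s·d) days. Hence:

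- Mean others on drug = Σ (d = 1 to 9) 2(10 − d)·max(0, 120 − s·d) / 1,200
- Mean not yet enrolled = Σ (d = 1 to 9) (10 − d)·min(120, s·d) / 1,200

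| s (days) | Mean others on drug | Peak others on drug | Mean not yet enrolled |
|---|---|---|---|
| 9 | 2 × 3,915 / 1,200 = 6.53 | 9 | 1,485 / 1,200 = 1.24 |
| 10 | 2 × 3,750 / 1,200 = 6.25 | 9 | 1,650 / 1,200 = 1.38 |
| 18 | 2 × 2,538 / 1,200 = 4.23 | 6 | 2,862 / 1,200 = 2.39 |
| 20 | 2 × 2,300 / 1,200 = 3.83 | 5 | 3,100 / 1,200 = 2.58 |

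As an example, for s = 20 the overlaps for d = 1 to 5 are 100, 80, 60, 40 and 20 days, and zero after that. So 9×100 + 8×80 + 7×60 + 6×40 + 5×20 = 2,300.

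**The case against.** The strongest reply is that nobody would apply the literal reading. For harm to follow, the investigator and the DSMB would have to pause the study for a Grade III event and decline to pause it for a worse one. The same DSMB receives the case anyway under 9.2, the patient is already off drug, and the IRB is told at once. This is one site with at most ten patients, and Section 9.4.1 contemplates immediate departures from the protocol to remove a hazard.

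The exposure counts also do not measure harm. They attach no probability to the event, and the time until DSMB review, which governs the added exposure, is not known. The cited rhabdomyolysis case was a liver-transplant recipient, and the reference title shows that he was also on tacrolimus. Transplant history is an exclusion here, and the protocol assigns that case no CTCAE grade.

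Most of this stands, and it limits the weight of the point: the omission is probably a slip, the affected patient is covered, and no endpoint or estimate changes. It does not close the gap. The DSMB recommendation in 9.2 concerns restarting that patient's drug, not whether the study continues. A suspension rule is written in advance so that the pause does not depend on interpretation on the day. If all agree on the intended meaning, it should be printed.

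**Conclusion.** The point holds. As written, the trial's only study-level safety trigger omits a non-fatal attributable Grade IV SAE, taking Grade III to mean CTCAE grade 3. It should be fixed, though it does not leave the affected patient unprotected.

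Under the stated assumptions, the automatic hold would be lost for an average of about four to six and a half other patients on drug, with a peak of five to nine, and for one to three not yet enrolled. The on-drug numbers fall if fewer than ten enroll or if patients have already stopped simvastatin.

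Two side points in 5.2.3 are matters of clarity only. Its restart text does not mention the DSMB, but it can be followed together with 9.2 and 7.2, so there is no conflict. It also says that for events of Grade 3 or above "the rules outlined in Sections 5.3 apply for holding of dose, dose reduction, removal from study and reporting requirements", yet no Section 5.3 exists. That is clerical, since the hold and reduction rules are printed in 5.2.3 itself.

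**What to change.** Reword the trigger in 7.2 to: *any death, or SAE of Grade 3 or higher attributable to the study agent*. The rest of 7.2 can stay, as can the description of serious events in 9.2.

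While amending, add one sentence to 5.2.3 saying that where 9.2 or 7.2 applies, restart at the Table 3 dose also needs the DSMB recommendation, and correct the cross-reference to Section 5.3.

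The cost is a few words in 7.2, plus one sentence and one reference in 5.2.3, with no new visits, tests or staff. The only operational effect is that an attributable Grade 4 SAE pauses the study until DSMB review, as a Grade 3 SAE already does.
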